Additionally, it would be important to analyze step counts from the pedometer and the percentage of days in which individual patients achieved prescribed targets. This would permit assessing whether any improvements in physical status resulted from the walking intervention. Conversely, if there is no improvement in physical status assessments, we could diagnose if nonadherence with the walking prescription was the reason. Finally, it would be helpful in guiding future research to calculate the time and cost required to recruit eligible patients as well as to assess patient satisfaction with the walking prescription.

INVESTIGATOR STUDY PLAN - REQUIRED

We therefore propose a study of 400 older adults scheduled for surgery with the following aims which will prepare us to conduct a larger trial focused on clinical outcomes.

Aim 1: To assess the impact of a walking prescription intervention on outcomes of endurance, balance, gait speed, strength, and self-reported function in patients with frailty.

Aim 1a: To estimate improvement in outcomes as a function of duration of the walking intervention.

Aim 1b: To re-estimate the effect of the intervention adjusting for the percentage of days each patient met his/her walking goal.

Aim 1c: To measure patient satisfaction with the walking intervention.

Aim 2: To measure the average time and cost required to recruit and follow up each patient.

Aim 3: Postoperative outcomes: we may also measure several postoperative outcomes

Change in six-minute walk distance from baseline

The number of steps per day in the hospital

Time to 100 steps at the day of discharge.

Discharge to skilled nursing facility

Length of stay

Thirty-day outcomes including serious complication, readmission, and death

Aim 4: Measure the performance of Edmonton frailty score for predicting 30 day outcomes including serious complication, readmission, death.

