Aim 1a: Self-reported function: We will administer the 12 items of the Veteran Rand (VR-12) in order to measure self-reported function.¹⁶ We will then calculate the summary physical component score (PCS) using a published algorithm.¹⁶ The algorithm norms PCS to range between 0 and 100, with 50 as a mean, and 10 as the standard deviation for the US population.

Aim 1b: Adherence with exercise: We will measure the percentage of days in which the participant meets his/her step count target for intervention patients and activity journals for both groups of patients

Aim 1b: Patient satisfaction: We will design a custom instrument to assess patient satisfaction with our intervention.

Aim 2: Time and cost to recruit 400 frail older adults: We will calculate the time and cost to recruit 400 patients. We will assess time in multiple ways: number of calendar days and number of working clinic days. For cost, we will assign an hourly wage for research staff member and RN efforts and then multiply by the number of hours required to perform recruitment, follow-up telephone calls, and follow-up assessments.

Aim 3: Postoperative outcomes: we may also measure several postoperative outcomes, including:

Change in six-minute walk distance from baseline

The number of steps per day in the hospital

Time to 100 steps at the day of discharge.

Discharge to skilled nursing facility

INVESTIGATOR STUDY PLAN - REQUIRED

Length of stay

Postoperative Recovery (measured via quality of recovery scale, abdominal surgery impact scale)

Thirty-day outcomes including serious complication, readmission, and death

Aim 4: Thirty-day outcomes including serious complication, readmission, and death

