Participants may walk steps over the course of a day or in one session. The initial walking prescription will also provide instructions to the participant to increase his/her number of steps each week by 10 to 20%.

A research staff member will then orient the participant to the pedometer

Weekly calls: During the interim between the day of consultation until the day of surgery, a study staff member will make weekly calls to each patient. The calls will provide participants an opportunity to report any symptoms which could warrant stopping the walking regimen and/or seeking urgent medical attention. In addition, we will train the study staff member to troubleshoot any problems setting step count targets or other problems with the pedometer. In cases in which the pedometer fails, we will budget to have additional pedometers available to mail to the patient.

Activity log: we will ask participants to log all of their physical activities-date, activity type, number of minutes. We will submit a copy of the activity log to the irb for approval prior to recruiting randomized participants to complete it.

Control subjects: a study staff member will provide general walking advice with typical warnings about when to stop (e.g., chest pain, breathing difficulty, or fall). Control subjects will receive no other intervention. We will also ask control subjects to log their physical activities.

Preoperative assessment: On the day of preoperative testing, which will usually occur three to five weeks after the baseline measurement, a research staff member or other project staff member will collect the pedometer and record the repeat physical status assessments (6MWD and SPPB). On the day of surgery, we may also place a research grade monitor on patients so as to track their steps while in the hospital.

Hospital period assessment: By the day of discharge, we will collect the research grade monitors and repeat our physical status measurements.

INVESTIGATOR STUDY PLAN - REQUIRED

In order to test the above procedures in the randomized individuals, we will enroll up to 15 patients as test patients. All these patients will undergo screening, baseline assessment/interview, follow-up assessment on day of preoperative testing, in-hospital step tracking and Hospital period assessment.

30 day assessment: Approximately 30 days from day of surgery, at office of surgery clinic, we will repeat our physical status measurements

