12. DATA AND SPECIMEN BANKING*

No specimens are being collected as part of the research. Data will not be banked for use in future research outside of the scope of this study.

13. Data Analysis and Management

Analysis As a first step, we will examine the distributions of all variables using histograms and summary statistics for continuous variables, and frequencies for categorical variables. We will consider transformations to enhance normality where continuous variables demonstrate substantial skew or outliers.

Aim 1: We will calculate the distribution of within-participant change for each of the five physical status measures and assess the average and median change against the minimal clinically important difference (MCID) for each assessment, as well as the percentage of patients with a minimal clinically important difference. In cases where a MCID is not available we will decide among our expert advisory team members the threshold values that indicate some important improvement. In our analysis we will also examine the role of baseline assessment on the amount of improvement by using a generalized linear model for the outcome of change in physical status controlling for baseline assessment.

Aim 1a: In this aim, we will examine the association of duration of time available for the intervention with within-participant change in physical status outcomes, using nonparametric locally-weighted scatterplot smoothing (LOESS) regression.¹⁷ We will rerun our generalized linear model controlling for duration of time available for the intervention, transforming the duration variable if indicated by the LOESS plots, e.g., piecewise linear if a threshold effect is seen.

Aim 1b: Similar to Aim 1a analyses, we will examine the association of percentage of days (of the 30 days available in pedometer memory), the step count target was met with within-participant change in physical status outcomes, again using LOESS plots. We will rerun our generalized linear model controlling for the percentage of days in which the patient met their step count target, transforming the percentage of days if indicated by the LOESS plots.

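### The Aim 1b adherence percentage refers to a 30-day pedometer memory, but the walking window is usually 21 to 35 days: read as a fixed base it caps short-window patients, and on either reading days past the memory are lost

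*Combined protocol and SAP*

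**What the plan says.** Section 13 (Data Analysis and Management), Aim 1b, relates change in physical status to the "percentage of days (of the 30 days available in pedometer memory") on which the step target was met. It continues: "We will rerun our generalized linear model controlling for the percentage of days in which the patient met their step count target". That second statement has no 30 in it.

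Section 4 (Objectives) describes the same analysis as "adjusting for the percentage of days each patient met his/her walking goal", and Section 10 (Study Endpoints) says: "We will measure the percentage of days in which the participant meets his/her step count target for intervention patients". Neither mentions a 30-day base.

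Section 11 (Procedures Involved) sets the length of the window. Preoperative testing is the visit "which will usually occur three to five weeks after the baseline measurement", and at that visit staff "will collect the pedometer and record the repeat physical status assessments (6MWD and SPPB"). The weekly calls in Section 11 cover symptoms and problems with targets or the device. No download or recording of step data before collection is described.

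Duration has its own analysis under Aim 1a: "We will rerun our generalized linear model controlling for duration of time available for the intervention". The plan does not say whether duration stays in the model when Aim 1b is run.

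**The concern.** The 30-day memory does not match a window that usually runs from three to five weeks. Section 13 does not say how to score a window shorter than 30 days or what becomes of days beyond the memory. Two analysts following it could score the same fully adherent 21-day patient at 70% or at 100%, and the choice could be made after the data are seen.

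The score has a diagnostic role. Section 4 wants it to show whether any improvement came from the walking and, if there is none, whether nonadherence was the reason. A score capped by a short window would label fully adherent patients as partly nonadherent. Because Aims 1a and 1b are separate reruns of one model, an effect of duration could also appear as an effect of adherence. The results are meant to prepare a larger trial.

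**Working it through.** **Inputs from the documents.** Memory: 30 days (Section 13). Window from baseline to collection: 3 to 5 weeks, so 3 × 7 = 21 to 5 × 7 = 35 days (Section 11). A possible threshold at 1 to 2 weeks, 7 to 14 days, is also of interest (Section 4). Step targets rise by 10 to 20% each week (Section 11). The plan states no adherence figure, so there is none to reproduce first.

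**Reading A: 30 is the denominator for every patient.** For a window of L days, the highest possible score is min(L, 30)/30.

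| Window (days) | Highest possible score | Score if target met on 70% of days |
|---|---|---|
| 7 | 7/30 = 23.3% | 16.3% |
| 14 | 14/30 = 46.7% | 32.7% |
| 21 | 21/30 = 70.0% | 49.0% |
| 28 | 28/30 = 93.3% | 65.3% |
| 30 | 30/30 = 100% | 70.0% |
| 35 | 30/30 = 100% | 70.0% |

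The dependence on duration arises only below 30 days.

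The strength of the link depends on distributions that the documents do not give. Assume whole-day windows uniform on 21 to 35 and true adherence unrelated to duration. The correlation of (days met/30) with duration is then:

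| Assumed true adherence, mean (SD between patients) | Correlation | Squared |
|---|---|---|
| 0.60 (0.20) | 0.29 | 0.08 |
| 0.70 (0) | 0.65 | 0.42 |
| 0.70 (0.10) | 0.50 | 0.25 |
| 0.70 (0.20) | 0.34 | 0.11 |
| 0.50 (0.25) | 0.21 | 0.04 |

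In the first row the measured mean is 0.60 × 21/30 = 42% at 21 days and 60% at 30 days or more, although true adherence is 60% throughout.

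**Reading B: 30 is only the memory limit, and the denominator is the patient's own recorded days, at most 30.** Full adherence scores 100% at every window length, and the simulated correlation with duration is about 0. What remains is truncation: days lost = max(0, L − 30).

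- L = 31: 1 day, 1/31 = 3.2% of the window.
- L = 35: 5 days, 5/35 = 14.3% of the window.
- With uniform windows of 21 to 35 days, 5 of 15 lengths lose any days, and the average loss is (1 + 2 + 3 + 4 + 5)/15 = 1 day per patient.

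If the memory keeps the most recent days, which is an assumption, the lost days are the earliest. Because targets rise weekly, those are the days with the lowest targets.

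**The case against.** The strongest objection is that Section 13 never says to divide by 30 for everyone. The parenthesis can be read as a device limit on which days can be retrieved, and a patient with a 21-day window does not have 30 walking days to retrieve. Three of the four statements of the measure (Section 4, Section 10 and the later sentence in Section 13) give a plain percentage of days. This stands. A reader might infer that adherence as planned simply is in part a measure of duration. The documents do not support that as a settled fact, because it follows only under Reading A.

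It also stands that the correlations rest on assumed distributions, that 0.29 is only about 8% shared variance, and that Aim 1b is explanatory. The denominator could still be set at analysis from retained data and dates; only days past the memory cannot be recovered. The loss of early, low-target days depends on how the device overwrites data, which the documents do not state.

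Two replies limit the objection. First, Section 13 is the only analysis definition, and its literal wording names 30 as the base. Second, keeping duration in the model would not fully repair a fixed base: the cap multiplies the score, so a true difference of 10 points between two 21-day patients is recorded as 10 × 21/30 = 7 points.

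A further fair point concerns the remedy. Dividing by all calendar days would count device failure and non-wear as nonadherence, although Section 11 anticipates failures and mailed replacements. The fix allows for this.

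**Conclusion.** The concern holds in conditional form. The denominator is not settled for windows other than 30 days. On the literal reading, adherence is capped at 70% for 21 days and 93% for 28 days and is mechanically tied to duration, with an illustrative correlation of about 0.2 to 0.65. On the other reading there is no such link, but windows of 31 to 35 days lose 3% to 14% of their days. The ceilings and day counts are arithmetic from Sections 11 and 13. The correlations rest on uniform windows and on adherence unrelated to duration. This should be corrected before data collection: the aim is secondary, but the literal rule can give the wrong diagnosis of nonadherence, and days overwritten in the device may not be recoverable.

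**What to change.** In Section 13, replace the 30-day base. Define adherence as days on target divided by that patient's own days with a working pedometer, from first prescription to the day before preoperative testing. Report device-failure and non-wear days separately, so that they are neither counted as nonadherence nor hidden.

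In Section 11, add the recording of step data to the weekly calls already planned, so that days beyond the memory are kept.

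In the Aim 1b model, include duration as a covariate, so that adherence and duration are estimated together.

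The cost is a short text change in two sections and slightly longer calls. The drawback is that some step values will be read out by patients rather than downloaded; these should be flagged in the data.

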Descriptive variables / covariates. We will collect basic demographic information (age, race, and gender), comorbidity, body mass index information, and surgical information including principal CPT code for surgical procedure and anesthesia type. We will also assess exercise self-efficacy using a modified version of the exercise self-efficacy scale.¹ Exercise self-efficacy is the belief that a patient can exercise targeted amounts without additional assistance from others. Assessing for this will allow us to control for baseline difference in the intervention and control patients that might impact on our interpretation of the efficacy of the intervention. The instrument is a simple inventory of items questioning if a patient can accomplish exercise target under various circumstances. A copy of the instrument has been included with the protocol submission.

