“After the first minute, tell the patient the following (in even tones): “You are doing well. You have 5 minutes to go.” When the timer shows 4 minutes remaining, tell the patient the following: “Keep up the good work. You have 4 minutes to go.” When the timer shows 3 minutes remaining, tell the patient the following: “You are doing well. You are halfway done.” When the timer shows 2 minutes remaining, tell the patient the following: “Keep up the good work. You have only 2 minutes left.” When the timer shows only 1 minute remaining, tell the patient: “You are doing well. You have only 1 minute to go.” Do not use other words of encouragement (or body language to speed up). If the patient stops walking during the test and needs a rest, say this: “You can lean against the wall if you would like; then continue walking whenever you feel able.” Do not stop the timer. If the patient stops before the 6 minutes are up and refuses to continue (or you decide that they should not continue), wheel the chair over for the patient to sit on, discontinue the walk, and note on the worksheet the distance, the time stopped, and the reason for stopping prematurely. When the timer is 15 seconds from completion, say this: “In a moment I’m going to tell you to stop. When I do, just stop right where you are and I will come to you.” When the timer rings (or buzzes), say this: “Stop!” Walk over to the patient. Consider taking the chair if they look exhausted. Mark the spot where they stopped.”

INVESTIGATOR STUDY PLAN - REQUIRED

Randomization: we will randomize patients in a 1:1 fashion into intervention and control groups using a prespecified table generated by our study statistician. More specifically we will use REDCap software to assign a study arm assignment using randomly permuted blocks of sizes 4 and 6.

Intervention patients: intervention patients will receive a walking prescription weekly calls from a study staff member as described below

Walking prescription: A study staff member in consultation with study physician (PI or co-I) will then provide the initial walking prescription based on the participants' baseline performance on the 6MWD following a published example^{12,13} and will focus the participant on walking at a moderate intensity (level of approximately 3 on the modified Borg Perceived Exertional Scale;¹⁴ laminated Borg scales will be distributed to participants).

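### Aim 1b promises an adherence-adjusted intervention effect, but days on target are measured only in the intervention arm, so section 13 can yield only a non-randomised association

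*Combined protocol and SAP*

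**What the plan says.** Section 4 states Aim 1b as "To re-estimate the effect of the intervention adjusting for the percentage of days each patient met his/her walking goal". The paragraph before the aims gives two uses for the step-count and target data. The first is causal: "This would permit assessing whether any improvements in physical status resulted from the walking intervention". The second applies after a null result: "if there is no improvement in physical status assessments, we could diagnose if nonadherence with the walking prescription was the reason".

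Section 10 defines the adherence measure as the percentage of days on which the participant "meets his/her step count target for intervention patients and activity journals for both groups of patients". The step-target percentage therefore belongs to the intervention arm, and only the journals cover both arms. Section 11 agrees. Allocation is described by "we will randomize patients in a 1:1 fashion into intervention and control groups". The walking prescription and pedometer orientation come under the intervention arm, while controls receive general walking advice and an activity log.

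Section 13 builds the Aim 1 model as change in physical status given the baseline value. For Aim 1b it plots change against the percentage of days on target with LOESS, and then: "We will rerun our generalized linear model controlling for the percentage of days in which the patient met their step count target". It names no term for randomised arm, no adherence value for controls and no use of the journals.

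**The concern.** The aim and the analysis do not describe the same quantity. Section 10, when it introduces exercise self-efficacy, treats efficacy as a comparison between arms: the score is collected to "control for baseline difference in the intervention and control patients that might impact on our interpretation of the efficacy of the intervention". On that meaning, Aim 1b asks for an arm effect adjusted for a variable that half the randomised patients do not have. On the other meaning, within-participant change, the regression can be fitted, but what it estimates is the relation between a behaviour chosen after randomisation and the outcome.

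The causal use in section 4 is what is at stake. A positive adherence slope is expected if walking improves physical status. It is equally expected if healthier or more motivated patients both meet their targets and improve more. The slope cannot separate the two, yet the results are meant to prepare a larger trial.

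**Working it through.** The plan gives no significance level, effect size or standard deviation for Aim 1b, so there is no stated figure to reproduce. The check has four steps.

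**1. Can an adherence-adjusted arm effect be estimated?** Add an arm term to the section 13 model: intercept, baseline value, arm, percentage of days on target. The percentage exists only where arm = 1, so among complete cases the arm column equals the intercept column. The design has 4 columns and rank 3, and the arm coefficient is not estimable.

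**2. Does coding controls as 0% help?** The plan does not propose this; it is the obvious workaround. Assumptions, none from the documents: change SD 60 m, adherence mean 60% and SD 20 points, no true effect of arm or adherence, and one omitted factor correlated r with both adherence and change.
- Spurious slope per unit of adherence: r² × 60 / 0.20 = 300r².
- Induced arm coefficient: −0.60 × 300r² = −180r².
- r = 0.2, 0.3, 0.5 gives −7.2, −16.2, −45.0 m when the truth is 0. Simulation gave about −7 to −8, −17 and −45 to −46 m.
- In the same simulations the randomised contrast (arm plus baseline, no adherence) averaged −0.5 to +0.1 m and rejected in 4.3% to 6.2% of trials.

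**3. How far could the intervention-arm slope mislead?** Under 1:1 allocation the intervention arm has 200/2 = 100 patients if 200 are randomised and 400/2 = 200 if 400 are. Section 24 gives a total of 200; sections 4 and 25 give 400. Assume no walking effect and one omitted factor, unrelated to baseline, correlated r with adherence and with change. The induced correlation between adherence and change is ρ = r². With one covariate in the model, z = √(n − 4) × atanh(ρ), and a two-sided 5% test rejects with probability Φ(z − 1.96) + Φ(−z − 1.96).

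| r | ρ | z, n = 100 | rejects | z, n = 200 | rejects |
|---|---|---|---|---|---|
| 0.2 | 0.04 | 9.80 × 0.0400 = 0.39 | 6.8% | 14 × 0.0400 = 0.56 | 8.7% |
| 0.3 | 0.09 | 9.80 × 0.0902 = 0.88 | 14.3% | 14 × 0.0902 = 1.26 | 24.4% |
| 0.4 | 0.16 | 9.80 × 0.1614 = 1.58 | 35.3% | 14 × 0.1614 = 2.26 | 61.8% |

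A simulation with adherence bounded between 0 and 100% (6,000 trials per setting) gave 7.3%, 14.1%, 34.1% and 8.6%, 23.1%, 61.3%. A larger sample makes the problem worse, because the bias stays while the standard error shrinks.

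**4. What if the factor is partly captured by baseline?** Let it correlate 0.7 with the baseline value, with baseline otherwise unrelated to adherence or change. Then ρ = r²(1 − 0.49) / (1 − 0.49r²). At r = 0.4, ρ = 0.0816 / 0.9216 = 0.0885, so z = 0.87 (n = 100) and 1.24 (n = 200), and rejection falls to about 14% and 24%. At r = 0.2 and 0.3 the rates are about 5.5% and 8% with 100 patients, and 6% and 10% with 200.

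**The case against.** The strongest reply is that section 13 already calls the LOESS step an association of days on target with within-participant change, so only two sentences in section 4 overreach. This stands in part. The analysis section is more careful than the aim, which is why the repair is mostly wording. But Aim 1b is a numbered aim, nothing labels it exploratory, and the causal use is stated outright.

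A second reply is that fitness is partly dealt with: section 11 scales the prescription to baseline six-minute walk performance, and the model adjusts for the baseline value. This also stands in part. Both reduce the fitness route, as step 4 of the working shows. Neither removes confounding by motivation or health.

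A third is that the plan states no test of the slope, so rejection rates measure something it does not promise. That is correct: the 5% test and the correlations are assumptions of this review. A reader might infer that Aim 1b would be falsely positive in a third or more of trials. The documents do not support that; those rates need r = 0.4 on both paths and a factor unrelated to baseline.

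A fourth is that no stated decision depends on the slope, since the interim rule uses change against the minimal clinically important difference. True, and it limits the consequence to interpretation.

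Finally, a reader might infer that adding exercise self-efficacy would cure the problem, since section 10 says "Exercise self-efficacy is the belief that a patient can exercise targeted amounts without additional assistance from others". Nothing shows that this score is the confounder or captures it fully.

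**Conclusion.** The concern holds in limited form. Aim 1b as worded cannot be delivered: the adherence-adjusted arm effect is not estimable because controls have no value, and the intervention-arm model gives a non-randomised association that cannot carry the causal use in section 4. This follows from the documents without assumptions. The size of any bias does not; the rejection rates in the working show direction and plausible range only.

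Three stronger readings should be set aside.
- The analysis is not uncomputable. It can be run in the intervention arm.
- Section 4's other use, checking for non-adherence after a null result, is not undermined. As a first check it needs the distribution of adherence, not the slope.
- A reader might take the 30 days of pedometer memory in section 13 as a fixed divisor that penalises shorter intervals. The wording reads more naturally as a device limit, so no fault is claimed there.

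The missing arm term in the base Aim 1 model is a related weakness that exists before adherence enters. It means that section 13 as written offers no randomised contrast to fall back on.

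**What to change.** In section 13, state that the intervention effect is the randomised arm contrast: arm term plus baseline value, no adherence term, in all randomised patients. State that the Aim 1b LOESS and generalized linear model are run in the intervention arm only and reported as a descriptive association between adherence and outcome.

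In section 4, reword Aim 1b and the sentence on whether gains can be attributed to the intervention so that they match. For the non-adherence question, report the adherence distribution in the intervention arm and logged activity minutes by arm, since both arms keep logs.

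Adding the exercise self-efficacy score to the Aim 1b model is optional and would reduce confounding only in part.

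The cost is wording in two sections; every variable is already collected. The price is that Aim 1b no longer claims a causal adherence-adjusted effect, and the descriptive association remains open to unmeasured confounding.

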Interim Analyses: Given the possibility that our walking intervention does not improve our physical status measures, we will perform the Aim 1 analysis after recruitment of each batch of 10 patients. More specifically, we will assess the average and median change against the MCID for each of the five measures. If we have not achieved the MCID for any of the measures after any one batch, we will work with our advisors, particularly [name], to revise our intervention (e.g. intensifying the walking regimen) with the goal of improving physical status more than the MCID of one or more measures by the time of the next interim analysis.

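### The interim rule can prompt revision of the randomised walking programme on immature, uncontrolled change data, and the Aim 1 to 1b models do not identify the version received

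*Combined protocol and SAP*

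**What the plan says.** Section 13, Interim Analyses: "we will perform the Aim 1 analysis after recruitment of each batch of 10 patients", and at each look "we will assess the average and median change against the MCID for each of the five measures". The condition for action is "If we have not achieved the MCID for any of the measures after any one batch". The team then consults its advisors about revising the intervention, with the goal of "improving physical status more than the MCID of one or more measures by the time of the next interim analysis".

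The analysis repeated at each look is defined earlier in Section 13. It is within-participant change set against the MCID, plus a "generalized linear model for the outcome of change in physical status controlling for baseline assessment". Aims 1a and 1b add only the time available and the percentage of days on target. No MCID value is listed: "In cases where a MCID is not available we will decide among our expert advisory team members the threshold values", with no date relative to the first look.

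Section 11 says "we will randomize patients in a 1:1 fashion into intervention and control groups", in permuted blocks of 4 and 6. The preoperative reassessment usually falls three to five weeks after baseline and consists of the 6MWD and the SPPB. VR-12 is taken at baseline and is next named at the six-month contact. Section 9 gives a two-year timeline. The total is 400 in Sections 4, 10 and 25, but 200 in Section 24 and in the Aim 2 analysis.

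**The concern.** Refining an intervention in a preparatory study is legitimate. The difficulty is the evidence on which this rule would do it. A look timed by recruitment finds few or no outcomes from the newest patients. A look at pre-post change alone credits the programme with improvement that would have happened anyway, although a concurrent control arm exists to measure exactly that. Small early samples can also miss the MCID on every measure when the programme works.

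If a revision follows, the Aim 1 to 1b models pool patients treated under different versions without a label. Section 4 says the study is to prepare a larger trial, so the investigators would need to know which version produced which result. Aim 1b is exposed in a further way: if a revision changes the step target, the percentage of days at target may not mean the same thing before and after.

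**Working it through.** The plan states no error rate or power for this rule, so there is no figure to reproduce.

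**1. Outcomes missing at a look.** Inputs: N of 200 or 400; a lag of 3 to 5 weeks (Section 11); even accrual over 52 or 104 weeks (assumed, within the two years of Section 9). Recruits without an outcome = lag × N / accrual weeks. Weeks to fill a batch = 10 × accrual weeks / N.

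| N | Accrual (weeks) | Batch fills in (weeks) | Recruits without an outcome |
|---|---|---|---|
| 200 | 104 | 5.2 | 5.8 to 9.6 |
| 200 | 52 | 2.6 | 11.5 to 19.2 |
| 400 | 104 | 2.6 | 11.5 to 19.2 |
| 400 | 52 | 1.3 | 23.1 to 38.5 |

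Where the last column exceeds 10, nobody in the newest batch has an outcome. Only the first row leaves any, at most 4 of 10. For that row, intervention completers at the first look number between floor((10 − 9.6)/2) = 0 and floor((10 − 5.8)/2) = 2.

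**2. Measures available.** The 6MWD gives endurance. The SPPB gives balance, gait speed and strength. Self-reported function needs VR-12, which is not listed preoperatively. At most four of the five can be judged.

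**3. Chance of a trigger.** Assumptions not in the plan: every recruit is randomised; about 5 intervention patients per batch (simulating the blocks gives exactly 5 in 64% of batches, range 3 to 7); normal change scores; MCID of 0.3 to 0.5 SD of change; means only; four equally correlated measures; cumulative data; constant effect; trigger = all four miss. N = 200 gives 20 batches. The last look comes when recruitment ends, leaving 19.

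At look j the mean of measure i is normal with mean μ_i and SD 1/√(5j), in SDs of change. The chance that all four means fall below the MCID at one or more looks was simulated.

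Hand check at look 1, zero correlation, all measures at 1.5 × an MCID of 0.3 SD: each misses with probability Φ(−0.15 × √5) = Φ(−0.335) = 0.369, and all four with 0.369⁴ = 0.018. Later looks add to this.

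| True change | Correlation 0.3 to 0.7 | Zero correlation |
|---|---|---|
| One at 2 × MCID, rest at MCID | about 7 to 30% | about 2 to 7% |
| All at 1.5 × MCID | 5 to 32% | 1 to 4% |
| All at 2 × MCID | under 1% to 13% | under 1% |

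About 85 to 100% of these first triggers fall in looks 1 to 4. The table treats every recruit's outcome as available. Counting completers only, the upper ends for correlation 0.3 to 0.7 become about 38%, 39% and 20%.

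**4. Lack of a control comparison.** Separate assumptions: five measures, SD of change 1.5 to 3 MCIDs, correlation 0.3 to 0.6, both arms improve by 0.5 MCID, and the intervention adds nothing. With 20 patients per arm, pre-post change in the intervention arm reaches the MCID on at least one measure in 20 to 61% of looks. The between-arm difference does so in 6 to 45%. With 5 intervention patients, the pre-post figure is 49 to 78%.

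**5. Precision after a revision.** The 95% half-width for an arm difference in 200 patients is 1.96 × √(2/100) = 0.28 SD. Within one version, if the change comes halfway, it is 1.96 × √(2/50) = 0.39 SD. Averaging two equal version strata gives 0.39/√2 = 0.28 SD.

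**The case against.** The strongest reply is that this is sensible early refinement. The plan says "we will work with our advisors", so a trigger opens a discussion and is not itself a revision. Most chance triggers come in the first 40 recruits, when adaptation costs least. The prescription is already individualised from the baseline 6MWD and rises weekly, so no fixed regimen is being lost. All of that stands, and it limits the size of the problem.

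Several stronger readings might be inferred, and the documents do not support them:

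- **Type I error inflation.** No test or stopping boundary is tied to the looks.
- **A biased arm comparison.** With concurrent controls, a version change does not bias a pooled arm difference. It makes that difference an average over versions, and only version-specific estimates lose precision.
- **Much higher false-trigger rates.** These arise if the true change sits exactly at the MCID, but a trigger there is not clearly an error, since the goal is to exceed the MCID. They also arise if each batch is judged alone, which is possible only if the look waits for that batch's outcomes.
- **Action whenever a single measure falls short.** The wording allows it, but the goal of one or more measures favours reading the trigger as no measure reaching its MCID.
- **No intention to compare arms at all.** Section 10 plans to control for baseline differences between intervention and control patients. The contrast is contemplated there but not written into the Aim 1 or interim analysis.

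Five intervention patients per batch is also an assumption. The plan does not say whether patients who are only screened, or the up to 15 non-randomised test patients, count towards a batch.

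**Conclusion.** The concern holds as a fault in the rule's evidence base and in version tracking. The timing problem needs only the plan's N, lag and timeline plus even accrual. The missing control comparison, fifth preoperative measure, arm term and version term can be read directly from Sections 11 and 13. These parts are firm.

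The trigger rates are illustrative. They range from under 1% to about a third across the above-MCID scenarios at correlation 0.3 to 0.7, are 7% or less at zero correlation, and are concentrated early. They show that chance triggers are plausible, not that revision is likely. The consequence is an Aim 1 result that averages over unlabelled versions, which is less useful for choosing what to take into the larger trial.

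**What to change.** Amend Interim Analyses in Section 13, with matching changes in Section 11:

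1. Time each look by a stated number of randomised patients per arm with completed preoperative assessments, and use all completed assessments to date.
2. Base the look on the between-arm difference in change for each re-measured outcome. Fix the thresholds before the first look and choose them to suit a between-arm difference, since an MCID for within-person change may not. State that the trigger is that no re-measured outcome reaches its threshold.
3. Record, for every patient in both arms, the version in force at randomisation and the date of any change. Flag patients mid-programme at a change. Report the Aim 1 arm difference stratified by version, both pooled and within version, and add version to the Aim 1a and 1b models.
4. Either add VR-12 to the preoperative assessment or state that looks use four measures.
5. State that changes made for safety are outside this rule.

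The number of completers per look and any cap on revisions are the sponsor's choice, and the content of any revision is for the investigators. More completers give fewer chance triggers but a later check: 50 per arm, for example, would use half of a 200-patient trial. The cost is later and fewer looks, protocol wording, two REDCap fields (version and change date) and, if chosen, one more VR-12 administration.
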